### **Security Assessments**

#### **Baseline Assessments:**

After signing the informed consent form, patients will be submitted to the baseline eligibility assessment (see Table 2).

Within 6 weeks of the first treatment dose: search for noraepinephrine expression by MIBG-I scintigraphy. If positive, eligibility is confirmed, and the following procedures are:

- Within 4 days of D1C1: Medical history, including previous diagnosis and treatment, history of other diseases (active and resolved), medications in use and general demographic data. Complete physical examination, ECOG performance index (PS) and vital signs.
- Within 4 days of the first treatment dose, laboratory tests will be performed: blood count, urea, creatinine, ALT, AST, total bilirubin, sodium, potassium, and pregnancy test for women of childbearing age; these patients will be oriented to contraception.
- Baseline imaging exams performed within 8 weeks of the first treatment dose will be accepted: CT scan (or MRI, if applicable) of the abdomen, pelvis and chest.
- For patients with functioning NET, it will be accepted that baseline tumor marker exams have been performed within 8 weeks of the first treatment dose (eg 5HIAA in 24-hour urine).

With the exception of MIBG scintigraphy, which is used routinely for patients with PggF (but not TNE), all of the above tests are already part of the routine in the treatment of NET at A.C.Camargo Cancer Center.

*Safety assessments during treatment:*

Patients will be evaluated clinically and with laboratory tests (Table 2) every 15 days between treatment cycles and after completion until resolution of any adverse treatment effects. +/- 3 days window will be allowed.

- Complete physical examination, measurement of vital signs, weight measurement, ECOG, use of medications.
- Assessment of adverse events.
- Laboratory evaluation: blood count, urea, creatinine, ALT, AST, total bilirubin, sodium, potassium, and others, if clinically indicated.

To grade toxicities we will use the CTCAE 5.0 criteria. Patients who have intolerable grade 2 or grade 3 toxicity that the investigator deems to be related to MIBG-1131 will have their treatment cycle delayed to grade 1 or resolution. If there is no reduction in the intensity of the adverse event to grade 1 within 8 weeks, treatment is discontinued.

All adverse effects will be graded and assessed whether or not they are related to treatment. If there is no CTCAE 5.0 classification for an adverse event, the degree of severity of mild, moderate, severe and life threatening will be used.

An adverse event for the purposes of this protocol is the appearance of (or worsening of pre-existing) undesirable sign(s), symptom(s) or medical condition(s) that occurs(s) after signature. informed consent, even if the event is not considered to be related to the drug(s) under study. The occurrence of adverse events should be obtained through indirect questions asked to the patient at each visit during the study. Adverse events can also be detected when they are reported voluntarily by the patient during or between visits or through physical examination, laboratory tests or other assessments.

Whenever possible, each adverse event should be assessed to determine:

1. Severity (mild, moderate, severe and life threatening) or (CTCAE 5.0 grade)
2. Its relationship to each drug under study (suspected / not suspected)
3. Its duration (initial and final dates or if they continue in the final exam)
4. Conduct adopted (no conduct adopted; study drug dosage adjusted/ temporarily interrupted; study drug permanently discontinued due to the referred adverse event; concomitant medication administered; non-drug therapy administered; hospitalization / prolonged hospitalization).

Patients requiring hospitalization should be immediately identified by the investigators in the study who monitor all patients.

*Criteria suspension of treatment:*

Patients may interrupt study treatment for one or more of the following reasons:

- Disease progression (documented by images and defined by the RECIST 1.1 criteria).

Clinical progression, based on the investigator's assessment

- Death.
- Intolerable or persistent adverse event (s) of grade 2 or higher.
- Withdrawal of consent by the patient.
- Need for new cancer therapy and / or surgery.

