## **Outcomes**

### **Primary:**

Disease control rate (DCR). Defined by absence of radiological progression in conventional imaging examinations by RECIST 1.1 at 6 months after the end of treatment. For patients with functioning syndrome, beside radiological DCR, patients should have improved in at least 10% of the baseline score of quality-of-life (EORTC QLQ-GINET21) and stability or decrease in tumor markers.

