### **Secondary:**

1- Disease control rate (DCR). Defined by absence of radiological progression in conventional imaging examinations by RECIST 1.1 at 3 months after the end of treatment. For patients with functioning syndrome, beside radiological DCR, patients should have improved in at least 10% of the baseline score of quality-of-life (EORTC QLQ-GINET21) and stability or decrease in tumor markers.

2- Progression-free survival. Defined by time from day 1 cycle 1 to death from any cause or radiological progression by RECIST 1.1, whichever occurs first. Patients alive and without progression at the time of study analysis will be censored for time-to-event analysis.

3- Radiological response rate. Assessed by RECIST 1.1 criteria.

4- Rate of Biochemical response. Defined by at least 30 percent drop in the tumor marker (24-hour urine 5-hydroxyindoleacetic acid (5-HIAA) and/or specific hormone), if functioning syndrome, at any time of treatment in relation to pre-treatment value.

5- Quality of life. Assessed by the EORTC QLQ-C30 and QLQ-GINET21; both available in Brazilian Portuguese. Improvement of at least 10% in the baseline score at 3 and 6 months after the end of the treatment will be considered clinically meaningful. Improvement by 10% of the baseline score at 3 and 6 months will be considered clinically meaningful.

6- Incidence of Treatment-related Adverse Events. Frequency of adverse events of grades 2 or more by Common Adverse Event Toxicity Criteria (CTCAE) version 5.0.

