## **Methodology**

### **Study design**

This is a single-arm, unicentric, single-stage, phase 2 clinical study of therapeutic metaiodobenzylguanidine (MIBG) for patients with metastatic well-differentiated neuroendocrine tumors and radiological progression or intolerance after standard lines of treatment and with MIBG-I positive scan.

Eligible patients will receive MIBG-I in up to 4 doses of 7,400Mbq (200 mCi) each, with an interval of at least 60 days. The administration of the cycles will depend on the results of the haematological exams, therefore, each patient will be able to receive from 1 to 4 cycles; In the experience of A.C.Camargo Cancer Center, most patients receive between 3 and 4 cycles. MIBG-I is administered intravenously to an inpatient, being discharged when reaching limits of radiological exposure recommended by the National Nuclear Energy Commission (invariably, 24 hours). The dose of 200mCi

per application for up to 4 doses of MIBG-I used in this protocol is the same used in routine at the institution and is also used in other PPRT treatments. This dose is safe and practiced by the service for at least a decade.

Clinical and toxicity assessments will take place every 2 weeks with medical history, physical examination and general laboratory until resolution of toxicities (usually 30 days after treatment). Imaging exams (chest, abdomen and pelvis CT scans) and 5-HIAA dosage in 24-hour urine (functioning tumors) will be performed at the beginning of treatment, and every 3 months until progression or exit from the study. Symptom assessment will be conducted using quality of life questionnaires that will be administered before treatment and every 3 months until progression. Toxicities will be measured in all medical visits through CTCAE version 5.0. Consultations, laboratory and imaging tests are already part of the treatment routine of these patients. The extra routine interventions, that is, the study, are the MIBG-I scintigraphy exam, the treatment with MIBG-I and the quality-of-life assessments.

Clinical data will be prospectively collected in an electronic database (REDCap) and will include sex, age, primary tumor site, performance scale status, functionality, metastatic disease duration, metastasis sites, degree of liver impairment, comorbidities, previous treatments, scores of quality of life results and toxicity.

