#### **Inclusion criteria**

- Age greater than or equal to 18 years.
- Well-differentiated metastatic NET from GEP, unknown primary with hepatic metastases or advanced/metastatic lung, inoperable, with no possibility of curative treatment.
- MIBG-I scintigraphy with positive expression in at least one lesion that presents significant uptake and compatible with therapeutic effectiveness.

- Disease with radiological progression (at least 10% tumor volume growth) in the last 12 months or with clinical and biochemical progression to functional NET according to clinical judgment.
- Progression or intolerance to previous standard treatments according to scenario (private [somatostatin analogue, everolimus] or public [somatostatin analogue]).
- Measurable disease.
- ECOG performance scale 0 to 2.
- Adequate organic function as defined by the following criteria:
  - Aspartate serum aminotransferase (AST), alanine serum aminotransferase (ALT)  $\leq$  2.5 times the upper limit of normal of the local laboratory (ULN-LL);
  - Total serum bilirubin  $\leq$  2.0 x ULN-LL;
  - Absolute neutrophil count  $\geq$  1,500/mm^3;
  - Platelet count  $\geq$  100,000/mm^3;
  - Hemoglobin  $\geq$  9.0 g/dL;
  - Estimated creatinine clearance using the MDRD equation  $\geq$  60ml/min
  - Informed consent form signed by the patient or legal representative.

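### In functional NET, the marker reading that established biochemical progression may also serve as the baseline, so regression to the mean can count as marker control or biochemical response

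*Combined protocol and SAP*

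**What the plan says.** All references are to the combined protocol and SAP.

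- **Entry.** Under Inclusion criteria, radiological progression is one route. The other is "or with clinical and biochemical progression to functional NET according to clinical judgment". No size of rise, number of readings or confirmation is set.
- **Baseline.** Under Baseline Assessments, for functioning NET, "it will be accepted that baseline tumor marker exams have been performed within 8 weeks of the first treatment dose". The scan that confirms eligibility has a shorter window ("Within 6 weeks of the first treatment dose: search for noraepinephrine expression"), so the accepted marker can predate it. The other baseline laboratory tests and the quality-of-life questionnaires must fall within 4 days of treatment.
- **Schedule elsewhere.** Study design says that imaging and urinary 5-HIAA "will be performed at the beginning of treatment, and every 3 months until progression or exit from the study". Table 2 lists the specific hormone under Baseline evaluation, not under Screening.
- **Use of the baseline.** For functioning syndrome, disease control at 6 months (primary outcome) and at 3 months (secondary outcome 1) requires "stability or decrease in tumor markers", together with radiological control and a GINET21 gain of at least 10%. Biochemical response (secondary outcome 4) is a drop of at least 30% "at any time of treatment in relation to pre-treatment value".
- **Design.** Single arm.

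**The concern.** A reading picked because it had risen lies, on average, above the patient's true level at that moment. The next reading then tends to be lower even if nothing has changed. If the picked reading is also the reference for change, that fall is scored as marker control or as response. A control arm selected in the same way would show the same fall and allow it to be subtracted; this trial has none. The fault is selection on the baseline value, and it arises whether or not earlier therapy carries over.

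At stake are one of the three conditions for primary success in functional patients and, more directly, the biochemical response rate, which has no second condition to hold it in check.

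**Working it through.** **The plan's own figures.** The plan gives no marker variability, no share of functional patients and no expected biochemical response, so there is no figure on this point to reproduce. The sample size of 22 concerns the disease control rate (40% versus 67%) and does not depend on this issue.

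**Does the text allow the overlap?** Entry may rest partly on a marker rise. The baseline may be any marker from the 8 weeks before dosing. Study design and Table 2 point to a sample at the start, but neither withdraws the 8-week allowance, and no sentence says that the baseline must differ from the qualifying reading. The overlap is therefore permitted, though not required.

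**How large can the effect be?** Assumptions, none of them from the documents:

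- Log-normal readings, within-patient CV 20% or 30%, independent errors.
- Entry when the qualifying reading is at least 25% above an earlier one.
- No drug effect.
- Stability read strictly as at or below baseline, because the plan sets no numerical limit.

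Log-scale SD: s = √ln(1 + CV²) = 0.198 (CV 20%) or 0.294 (CV 30%). The difference of two readings has SD s√2 = 0.280 or 0.415.

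*Flat true level, in closed form.* Let U = qualifying − earlier and V = qualifying − later, each divided by s√2. Their correlation is 0.5, because they share the qualifying reading.

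- Selection: U ≥ ln(1.25)/(s√2) = 0.223/0.280 = 0.80, or 0.223/0.415 = 0.54.
- At or below a reused baseline: P(V ≥ 0 | U ≥ 0.80) = 78%; P(V ≥ 0 | U ≥ 0.54) = 74%. With a fresh baseline: 50%.
- 30% drop: V ≥ −ln(0.7)/(s√2) = 0.357/0.280 = 1.27, or 0.357/0.415 = 0.86. Reused: 25% or 38%. Fresh: Φ(−1.27) = 10%, or Φ(−0.86) = 20%.

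Simulation with 2 million draws per setting gives the same values. It also gives the cases in which the true level really rose before the qualifying reading and then stayed there:

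| True change before qualifying reading | At or below baseline: reused (CV 20%, 30%) | Fresh | 30% drop at one reading: reused (CV 20%, 30%) | Fresh (CV 20%, 30%) |
|---|---|---|---|---|
| None | 78%, 74% | 50% | 25%, 38% | 10%, 20% |
| Sustained 50% rise | 59%, 61% | 50% | 13%, 26% | 10%, 20% |
| Sustained doubling | 52%, 55% | 50% | 11%, 22% | 10%, 20% |

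*Best of two readings, flat level.* A 30% drop at either of two later readings occurs in 40% to 56% with the reused baseline and 17% to 31% with a fresh one. Selection adds 40 − 17 = 23 to 56 − 31 = 25 points. The remaining 17% to 31% comes from taking the better of two unconfirmed readings.

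*Level still rising.* Let the true level rise 10% per step, with the fresh sample one step after the qualifying one and both judged at the same outcome reading one step later. At or below baseline is then 44% to 52% (reused) versus 37% to 41% (fresh), a gap of 8 to 11 points. The older baseline starts lower, which offsets part of the selection effect.

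**The case against.** The case for leaving the text alone has substance. Entry requires clinical as well as biochemical progression, so many qualifying rises will be real, and the table shows how quickly the effect shrinks when they are. The 8-week sentence is a permission, and Study design and Table 2 already indicate a sample at the start. All of this stands, and it limits the size. It does not close the gap, because a centre that follows the permission complies with the plan.

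Three stronger readings may tempt a reader, and the documents do not support them.

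- *The bias always favours MIBG.* If the marker is still climbing, a baseline up to 8 weeks old lies below the level at first dosing. That offsets the bias in part, and with a steep enough climb it works against MIBG.
- *The whole biochemical response rate is inflated.* Secondary outcome 4 covers every patient with functioning syndrome. Those who entered by radiological progression were not selected on the marker, and the split between routes is not given.
- *The primary disease control rate is inflated by the 24 to 28 points seen for the marker with a flat level.* Functional patients must also show radiological control and a GINET21 gain, the latter from its own baseline within 4 days of treatment. Non-functional patients are unaffected. The change in the overall rate cannot be computed from the documents and must be smaller than the change in the marker component.

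**Conclusion.** The concern holds in a limited form. The plan allows one reading both to qualify a functional patient and to serve as the reference for marker control and biochemical response, in a design with no comparator to remove the resulting regression to the mean.

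Under the stated assumptions, the excess at or below baseline is 24 to 28 percentage points if the true level was flat, 9 to 11 after a sustained 50% rise, and 2 to 5 after a doubling. The flat case is the extreme one. These figures apply only to biochemical-route patients whose qualifying sample is reused, and they depend on an assumed CV and qualifying rise. The biochemical response rate is the more exposed result; the effect on the primary rate is diluted. Nothing here changes the sample size. The correction is worth making because it is cheap and because an untreated baseline cannot be obtained once dosing has begun.

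**What to change.** Reconcile Baseline Assessments with Study design and Table 2. State that the baseline marker for the primary outcome and for secondary outcomes 1 and 4 is a new sample taken at the baseline visit, before the first dose. Preferably apply this to all functional patients, so that one baseline rule serves each endpoint. At minimum, state that the sample which established biochemical progression is never the baseline.

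For any patient already treated, report which baselines were qualifying samples and show the biochemical response rate with and without those patients.

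The cost is one sentence and one extra routine marker assay per affected patient. The change removes the selection effect only. False responses from taking the best of several unconfirmed readings remain and would need a separate rule, such as a confirmed drop.

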#### Effectiveness and Follow-up Assessments:

For evaluation of efficacy, patients will undergo imaging tests (chest, abdomen and pelvis tomography or abdomen and pelvis resonance) at baseline (within 8 weeks of starting treatment) and every 12 weeks (+/- 5 days) until progression or withdrawal from the study. Patients will also be evaluated for signs and symptoms that may be related to disease progression. Patients who present clinical progression, according to the investigator's judgment, but without radiological progression, will be able to discontinue the treatment and continue the image evaluation until progression; however, if new treatment is instituted, the last date of receipt of MIBG-I will be the censorship date in the progression-free survival analysis.

After documenting progression or leaving the study for other reasons, patients will be followed up by the investigator or another oncologist from the Clinical Oncology team for symptom control, image monitoring and possible future therapies. The patient continues to be cared for at the A.C.Camargo Cancer Center, if desired.

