Laboratory safety assessment												
Hemogram	X	X	X	X	X	X	X	X	X	X	X	
Urea/creatinine	X	X	X	X	X	X	X	X	X	X	X	
Bilirubin, AST/ALT	X	X	X	X	X	X	X	X	X	X	X	
NA, K	X	X	X	X	X	X	X	X	X	X	X	
Pregnancy test in women of childbearing age		X										
Image assessment												
CT of lung, abdomen and pelvis ***	X							X			X	X
Tumor marker **												
Specific hormone		X						X			X	X
Quality of life **												
EORTC QLQ-C30		X						X			X	X
EORTC QLQ-GINET21		X						X			X	X

IV, intravenous; MIBG, metaiodobenzylguanidine

\* within 6 weeks of the first dose and within 4 working days of D1;

\*\* window of +/- 3 days

\*\*\* baseline tests within 8 weeks of D1; Resonance of the abdomen and pelvis in special cases (allergy to iodinated contrast); window +/- 5 days

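### When new treatment follows clinical progression, PFS is censored at the last MIBG-I131 dose rather than at a tumour assessment, so PFS depends on dose count; the effect is small and confined to a secondary endpoint

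*Combined protocol and SAP*

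**What the plan says.** PFS is a secondary outcome: "Defined by time from day 1 cycle 1 to death from any cause or radiological progression by RECIST 1.1, whichever occurs first". The same item adds "Patients alive and without progression at the time of study analysis will be censored for time-to-event analysis" but names no censoring date. The Statistical plan adds only that time-to-event variables are reported by Kaplan-Meier.

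The one dated rule is under Effectiveness and Follow-up Assessments. Patients with clinical progression but no radiological progression may stop treatment and go on with imaging; "however, if new treatment is instituted, the last date of receipt of" MIBG-I131 "will be the censorship date in the progression-free survival analysis". Nothing elsewhere overrides it.

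The same section schedules imaging "every 12 weeks (+/- 5 days) until progression or withdrawal from the study". In Table 2 the row "CT of lung, abdomen and pelvis" is marked at weeks 12 and 24 and then periodically, while doses are marked at day 1 and weeks 8, 16 and 24. Under Study design, "each patient will be able to receive from 1 to 4 cycles". The reasons for interrupting study treatment include clinical progression, adverse events and "Need for new cancer therapy and / or surgery".

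**The concern.** A PFS censoring date should mark the last time the patient was known to be free of progression. Here that knowledge comes from 12-weekly scans, whereas the date of the last dose reflects marrow tolerance and when treatment stopped. Dosing ends by week 24 at the latest on Table 2, while scans continue. The rule can therefore discard clean scans taken after the last dose, or credit time after the last scan that no scan supports. Two patients with the same disease course can receive different PFS times because they received different numbers of doses.

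There is also a gap: no censoring date is given when new anticancer therapy starts without clinical progression. What is at stake is the PFS curve and median, which will be read descriptively.

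**Working it through.** The plan states no PFS target, event count or power, so there is no PFS figure of its own to reproduce. The 22 patients are sized on disease control rate.

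**Schedule check.** Doses are at weeks 0, 8, 16 and 24 (Table 2) and scans every 12 weeks (text). Study design asks for at least 60 days between doses, slightly more than Table 2's 8 weeks, and Table 2's last column reads every 12 or 8 weeks. Those passages need reconciling, but the point does not turn on them.

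| Doses (last dose) | Clean scans | New treatment | Censored at | Result |
|---|---|---|---|---|
| 1 (week 0) | 12, 24 | week 30 | week 0 | 24 − 0 = 24 weeks lost |
| 4 (week 24) | 36, 48 | week 50 | week 24 | 48 − 24 = 24 weeks lost |
| 4 (week 24) | 24 | week 26 | week 24 | nothing lost |
| 2 (week 8) | none yet | before week 12 | week 8 | 8 − 0 = 8 weeks unsupported |
| 3 (week 16) | 12 | before week 24 | week 16 | 16 − 12 = 4 weeks unsupported |

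**Illustration of size.** The documents do not say how many patients leave this way, so everything here is assumed:
- Failure times are exponential with a median of 13 months, the PFS that the Introduction cites for one retrospective series. λ = ln 2 / 13 months = 0.01226 per week and S(t) = exp(−λt), giving S(12) = 0.863, S(16) = 0.822, S(24) = 0.745, S(48) = 0.555.
- A share f = 20% of failures are clinical progressions followed at once by new treatment. The rest are radiological and dated at the next 12-week scan.
- Four doses are planned, and q = 1 − S(12) = 0.137.

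*Unlimited follow-up, closed form:*
- Last-scan censoring: [(1 − q)/(1 − fq)]⁴ = (0.863/0.973)⁴ = 62.0%.
- Plan's rule: h12 = (1 − f)q / [1 − f(1 − S(16))] = 0.1095/0.9644 = 0.1135; h24 = (1 − f)(S(12) − S(24)) / [fS(24) + (1 − f)S(12)] = 0.0945/0.8396 = 0.1125. From week 24 on, every eventual exit has left the risk set, so 48-week PFS = (1 − h12)(1 − h24)(1 − q)² = 0.8865 × 0.8875 × 0.745 = 58.6%.
- Gap: 62.0 − 58.6 = 3.4 points.
- All failures counted as events: S(48) = 55.5%.

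*Finite follow-up.* The Study time section plans recruitment over at most 2 years and a first assessment at 3 years, so follow-up runs from about 3 − 2 = 1 year (52 weeks) to 3 years (156 weeks). Patients who have not yet left stay in the risk set, so the closed form above overstates the gap. Simulation with 2,000,000 patients per scenario gives:

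| Follow-up | Plan, 4 doses | Last scan | Gap |
|---|---|---|---|
| Uniform 52–156 weeks | 60.4% | 62.0% | 1.6 |
| 48 weeks for all | 61.8% | 62.0% | about 0.3 (before rounding) |
| Unlimited | 58.6% | 62.0% | 3.4 |

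With 52–156 weeks of follow-up, one planned dose gives about 58.6% under the plan, so one dose against four differs by 60.4 − 58.6 = 1.8 points for the same disease course. With four doses and 10% exits, both rules put the median at the week-72 scan (16.6 months).

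**Against sampling error.** Ignoring censoring, the standard error of a 60.4% estimate in 22 patients is √(0.604 × 0.396/22) = 0.104, about 10 points.

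**The case against.** **Last-scan censoring is not closer to the truth.** In the illustration, counting every failure gives 55.5%, the plan gives 60.4% and last-scan censoring gives 62.0%. This objection stands. Patients who switch after clinical progression are probably doing worse than those who stay, so either censoring rule is informative, and the last-scan rule raises the curve more. The plan's relative closeness, however, comes from throwing away valid event-free follow-up, by an amount that varies with dose count. The answer is to report an analysis that counts these exits as events.

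**The rule may not reach patients who have finished treatment.** Its sentence concerns those who discontinue treatment for clinical progression, and a patient who completed four doses has nothing left to discontinue. This is a fair reading, and the week-50 example holds only if the rule covers such patients. If it covers exits only up to week 24, the share of exits losing a clean scan in this model is [S(12) − S(16)]/[1 − S(24)] = 0.0413/0.2549 = 16%. The one-dose example survives: a patient may stop early for clinical progression, continue imaging as the section allows, and switch months later.

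**A reader might infer a contradiction with the PFS definition.** There is none. The Outcomes section defines events and this section a censoring date.

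**A reader might also infer that every reason for interrupting treatment needs a censoring date.** It does not. Stopping MIBG-I131 alone leaves the patient under imaging until progression or withdrawal. Only new therapy started without clinical progression is left uncovered.

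**Conclusion.** The rule is wrong as written, but the consequence is limited. It ties PFS to the dosing record instead of to tumour assessment, can censor a patient at time zero despite later clean scans, and can credit 4 to 8 weeks that no scan supports. It affects a secondary endpoint with no hypothesis test.

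The size, about 1.6 points at 48 weeks, rests on an exponential model, a 13-month median, 20% exits, four doses and follow-up uniform over 52 to 156 weeks. It ranges from about 0.3 points (48 weeks of follow-up) to 3.4 points (unlimited follow-up), and all of these are small beside a standard error of about 10 points. The true number of affected patients is not in the documents.

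A reader might infer that the primary result is at risk. The documents do not support that: the rule is stated for the PFS analysis only, the sample size does not depend on it, and the Statistical plan states that all analyses are by intention to treat.

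**What to change.** Replace the rule under Effectiveness and Follow-up Assessments, and cross-refer to it from the PFS definition and the Statistical plan:

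- A patient who starts any new anticancer therapy before RECIST 1.1 progression or death, for whatever reason, is censored for PFS at the last adequate tumour assessment before that therapy, or at day 1 of cycle 1 if there is none after baseline.
- A pre-specified Kaplan-Meier analysis, always reported beside the first, counts clinical progression or the start of any new anticancer therapy as an event on its date.

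The second sentence is essential, because last-scan censoring alone tends to raise the curve. The first also closes the gap for new therapy started without clinical progression and removes the doubt about patients who have completed treatment.

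The cost is two sentences, one extra analysis and two PFS estimates to explain. No extra visits, scans or patients are needed. The dates of clinical progression and of new therapy should be confirmed as database fields.
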